8.1.3.1.1. Dose Interruption and Modification for Nonhematologic Toxicities

Dosing modifications for nonhematologic toxicities are provided in [Table 6](#). TAS-120 will be held when the dose interruption criteria are met.

Table 6: TAS-120 Dosing Modification for Nonhematologic Toxicities

Grade^a	Dose Interruption/Resumption	Dose Adjustment
Grade 1 or 2	Maintain treatment at the same dose level, except for Grade 2 elevations of bilirubin, AST, and ALT, which should be managed as described in Table 9 .	None
Grade 3 ^{b,c}	Suspend treatment until return to Baseline or Grade \leq 1	Reduce by 1 dose level ^c from the previous level
Grade 4 ^d	Suspend treatment until return to Baseline or Grade \leq 1	Permanent Discontinuation of TAS-120

- a. At the discretion of the investigator, patients may continue/discontinue on TAS-120 at the same dose with/without reduction or interruption for AEs (irrespective of grade) considered unlikely to become serious or life-threatening (including, but not limited to, fatigue and dry skin).
- b. Except for Grade 3 nausea and/or vomiting controlled by aggressive antiemetic therapy or Grade 3 diarrhea responsive to antidiarrheal medication which does not require dose hold or dose reduction.
- c. See [Table 5](#) for recommended dose level reductions.
- d. Grade 4 non-hematologic laboratory abnormality: TAS-120 will be permanently discontinued if it is assessed by the Investigator as life threatening.

Recommendations for hyperphosphatemia management are provided in [Table 7](#). These are suggested guidelines based on emerging data from studies evaluating FGFR inhibitors, and from experience of participating investigators. However, clinical judgment from treating physicians and local standard practices should be followed to decide the best management for the patient.

Table 7: Recommendations for Hyperphosphatemia Management

Serum Phosphorus Result ^a (mg/dL and mmol/L) ^b	Grade ^c	TAS-120 Dose Interruption and Modification	Recommended phosphate binder for the management of hyperphosphatemia ^d
ULN < P < 5.5 (mg/dL) ULN < P < 1.78 (mmol/L)	Grade 1	
 No Interruption, consider phosphate binder once serum phosphorus level is > ULN Should serum phosphorus level rapidly increase within 1 week, consider early phosphate lowering therapy, eg, Sevelamer oral tablets 800 mg TID 	
 800 mg tablets Sevelamer TID 1600 mg tablets Sevelamer TID 2400 mg tablets Sevelamer TID
5.5 ≤ P ≤ 7.0 (mg/dL) 1.78 ≤ P ≤ 2.26 (mmol/L)	Grade 2	
 No interruption, implement phosphate binder (monotherapy or in combination) Start with Sevelamer monotherapy (range from 800 mg TID to 2400 mg TID). Re-assess serum phosphate within 7 days, and plan to escalate Sevelamer or add treatment with acetazolamide 250 mg QD or TID and/or lanthanum carbonate 1.0 g QD or TID, and further titration, if phosphate level continues to increase. 	
 Acetazolamide 250 mg QD (and titrate up to BID or TID if required) Lanthanum carbonate (Fosrenol) 1.0 g QD (and titrate up to BID or TID if required)^e
7.0 < P ≤ 10.0 (mg/dL) 2.26 < P ≤ 3.23 (mmol/L)	Grade 3	
 Dose reduce TAS-120 to the next lower dose level and intensify phosphate lowering therapy. If serum phosphorus level has resolved to ≤ Grade 2 within 14 days after dose reduction, continue TAS-120 at the same dose level. If serum phosphorus level not resolved to ≤ Grade 2 after 14 days, further reduce TAS-120 from the last reduced dose level (or no lower than 12 mg) If serum phosphorus level not resolved to ≤ Grade 2 after 14 days of the second dose reduction of TAS-120 (or no lower than 12 mg), dose interrupt TAS-120 until it is resolved to ≤ Grade 2 before resuming TAS-120 at the reduced dose prior to dose interruption. 	
P > 10.0 (mg/dL) P > 3.23 (mmol/L)	Grade 4	Interrupt TAS-120 until serum phosphorus level is resolved to ≤ Grade 2, then resume TAS-120 at the next lower dose level and intensify phosphate lowering therapy. If after 2 dose interruptions and 2 dose reductions, serum phosphorus level is not resolved to ≤ Grade 2 after 14 days, permanently discontinue TAS-120.	

Abbreviations: BID = twice a day; P = Phosphorus; QD = once a day; TID = three times a day; ULN = upper limit of normal

- Serum phosphorus will be tested 4 days (± 24 hours) after Day 1 of Cycle 1 to initiate early intervention for hyperphosphatemia.
- mmol/L = mg/dL x 0.3229 (conversion factor)
- This grading for the range of serum phosphorus levels will be used for the protocol.
- Phosphate binder can be used as monotherapy or in combination. Please consult the drug package insert. Sevelamer should be preferably taken in the middle of meals, both tablets and powder, in order to improve gastrointestinal tolerance and compliance. If Sevelamer cannot be used, other Phosphate binders or hyperphosphatemia treatment drugs can be used. Lanthanum carbonate should be taken instead just after meals – tablets of Fosrenol® are quite big, but can be cut if required. No dose adjustments are needed in patients with renal or hepatic impairment.
- Titrate the dose every 2-3 weeks until an acceptable serum phosphate level is reached.

If there is any uncertainty about continuing therapy or resuming therapy in a patient with Grade ≥ 3 nonhematologic AEs, the case must be discussed with the Sponsor’s Medical Monitor prior to continuing TAS-120.

8.1.3.1.2. Dose Interruption and Resumption Criteria for Hematologic Toxicities

Criteria for dose interruption and resumption for hematologic toxicities are described in [Table 8](#).

Table 8: TAS-120 Dose Interruption and Modification Criteria for Hematologic Toxicities

Recommended Dose Modifications for TAS-120	
Worst toxicity CTCAE Grade (value)	Recommended dose modification any time during a cycle of TAS-120
Anemia (Hgb)	
Grade 1 (Hgb < LLN - 10.0 g/dL)	Maintain dose level
Grade 2 (Hgb < 10 - 8.0 g/dL)	Maintain dose level
Grade 3 (Hgb < 8.0 - 6.5 g/dL)	Withhold dose until resolved to \leq Grade 1 or baseline, 
 • If resolved \leq 7 days, then maintain dose level • If resolved $>$ 7 days, then reduce 1 dose level
Grade 4 (life threatening consequences; urgent intervention indicated)	Withhold dose until resolved to \leq Grade 1 or baseline, then reduce 1 dose level
Neutropenia (ANC)	
Grade 1 (ANC < LLN - 1500/mm ³)	Maintain dose level
Grade 2 (ANC < 1500 - 1000/mm ³)	Maintain dose level
Grade 3 (ANC < 1000 - 500/mm ³)	Maintain dose level
Grade 4 (ANC < 500/mm ³)	Withhold dose until resolved to \leq Grade 2 or baseline, 
 • If resolved \leq 7 days, then maintain dose level • If resolved $>$ 7 days, then reduce 1 dose level
Febrile neutropenia (ANC < 1.0 x 10 ⁹ /L, fever \geq 38.5°C)	Withhold dose until resolved, then reduce 1 dose level
Thrombocytopenia	
Grade 1 (PLT < LLN - 75,000/mm ³)	Maintain dose level
Grade 2 (PLT < 75,000 - 50,000/mm ³)	Maintain dose level
Grade 3 (PLT < 50,000 - 25,000/mm ³)	Withhold dose until resolved to \leq Grade 1 or baseline, 
 • If resolved \leq 7 days, then maintain dose level • If resolved $>$ 7 days, then reduce 1 dose level
Grade 4 (PLT < 25,000/mm ³)	Withhold dose until resolved to \leq Grade 1 or baseline, then reduce 1 dose level
Abbreviations: ANC = absolute neutrophil count; Hgb = hemoglobin; LLN = lower limit of normal; PLT = platelets	

If the TAS-120 dose is reduced, the dose will not be increased upon resumption. If a benefit/risk assessment favors the increase of dose up to the initial starting dose after dose reduction, an agreement with the Sponsor’s Medical Monitor needs to be made prior to the dose increase.

If the toxicities requiring dose reduction as defined above do not recover based on the criteria defined in [Table 6](#) through [Table 8](#) within the 21 days of the last dose of TAS-120, the patient

will be discontinued permanently from the study. If resumption criteria are met within 21 days of the last dose of TAS-120, the patient can resume TAS-120 treatment at the appropriate dose level according to instructions provided in [Section 9.1.3.1](#), TAS-120 Dose Reductions for Treatment-emergent Toxicities.

Treatment-emergent toxicities should be followed until stabilization according to [Table 9](#).

Table 9: Required Follow-up for Toxicities

Toxicity	Follow-up evaluation
Hematology	If \geq CTCAE grade 3 neutropenia or \geq CTCAE grade 3 thrombocytopenia have been demonstrated, these parameters must be repeated at least twice a week until resolution to \leq CTCAE grade 1 or baseline to allow for initiation of re-treatment, and then at least weekly until either initiation of retreatment or until stabilization.
Renal	If creatinine clearance (calculated* or measured value**) < 30 mL/min has been demonstrated, this parameter must be repeated at least twice a week until resolution to baseline to allow for initiation of re-treatment, and then at least weekly until either initiation of re-treatment or until stabilization.
Hepatic	If bilirubin ≥ 2 x ULN or \geq CTCAE grade 3 ALT or AST or the combination of \geq CTCAE grade 2 bilirubin and \geq CTCAE grade 2 ALT or AST elevation has been demonstrated, these parameters must be repeated at least twice a week until resolution to \leq CTCAE grade 1 or baseline to allow for initiation of re-treatment, and then at least weekly until either initiation of re-treatment or until stabilization. Patients with total bilirubin $> 1.5 \times$ ULN, or > 3.0 mg/dL for patients with Gilbert's syndrome (any duration) should have fractionation of bilirubin into total/direct or indirect/direct components and any additional work-up as clinically indicated by these results. Follow-up of hyperbilirubinemia should proceed as per the guidelines above, irrespective of the results of fractionation.
Cardiac	If at any time a QTcF > 480 ms and ≤ 500 ms is observed, a cardiology consultation must be sought to re-evaluate the abnormal ECG finding. If at any time a QTcF > 500 ms is observed, 1) Triplicate ECGs (2-3 minutes apart) need to be taken approximately 1 hour after the initial ECG. 2) If the mean QTcF is > 500 ms, the patient must postpone study treatment until a cardiologist has re-evaluated the ECG. 3) The re-evaluation of ECG needs to be done as soon as practical but within 7 days of the initial abnormal ECG. 4) If the cardiologist confirms a mean QTcF > 500 ms, the patient must be discontinued permanently from study.
Non-laboratory	Patients who experience non-laboratory Grade 3 or 4 AEs must be evaluated at least once a week following demonstration of the resolution of the toxicity to allow for re-treatment, until stabilization of the toxicity, or until study completion.

Abbreviations: AE = adverse event; ALT = alanine aminotransferase; AST = aspartate aminotransferase
CTCAE = Common Terminology Criteria for Adverse Events; ECG = electrocardiogram; ms = milliseconds;
QTcF = Fridericia's corrected QT interval; ULN = upper limit of normal

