11.2. Laboratory Evaluations

11.2.1. Reporting and Evaluation of Laboratory Test Results

Laboratory tests will be performed as required per protocol. All laboratory values that are out of the normal range will be evaluated for their clinical significance before exposing the patient to the next dose of TAS-120.

The laboratory must provide normal reference ranges.

Any laboratory abnormality that has a clinical impact on the patient (e.g., results in delay of TAS-120 dosing, study discontinuation) must be reported as an AE, unless it is considered a supporting lab to a clinical diagnosis that is already reported as an AE. Febrile neutropenia must be reported as an AE and is defined as an ANC < 1 000/mm³ with a single body temperature of > 38.3°C (101°F) or a sustained temperature of ≥ 38°C (100.4°F) for more than 1 hour. All laboratory data will be analyzed using NCI CTCAE grade criteria (version 4.03).

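### Protocol Tables 6, 8 and 9 do not agree: the referral of Grade 2 liver elevations leads to no dosing instruction, and two neutrophil recovery levels are tied to re-treatment

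*Protocol*

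**What the plan says.** **Liver.** In Protocol 8.1.3.1.1, the Grade 1 or 2 row of Table 6 keeps treatment at the same dose level, "except for Grade 2 elevations of bilirubin, AST, and ALT, which should be managed as described in" Table 9. The Dose Adjustment cell of that row reads None. The Hepatic row of Table 9 (Protocol 8.1.3.1.2) has three triggers: bilirubin at least 2 × ULN; ALT or AST of Grade 3 or higher; or bilirubin of Grade 2 or higher together with "CTCAE grade 2 ALT or AST elevation has been demonstrated, these parameters must be repeated at least twice a week until resolution to" Grade 1 or lower, or baseline. It adds fractionation and work-up when total bilirubin exceeds 1.5 × ULN (3.0 mg/dL in Gilbert's syndrome).

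**Neutropenia.** Table 8 (Protocol 8.1.3.1.2) has the row "Grade 3 (ANC < 1000 - 500/mm ³) Maintain dose level". After Grade 4 it withholds until recovery to at most "Grade 2 or baseline". The dose is then kept if that took 7 days or less, and reduced one level if it took longer. The Hematology row of Table 9 starts at Grade 3 neutropenia or thrombocytopenia and asks for at least twice-weekly repeats until at most CTCAE "grade 1 or baseline to allow for initiation of re-treatment, and then at least weekly until either initiation of retreatment or until stabilization".

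**Febrile neutropenia.** Table 8 describes it as ANC below 1.0 × 10⁹/L with fever of 38.5°C or more, and withholds then reduces. Protocol 11.2.1 defines it for AE reporting as ANC below 1000/mm³ "with a single body temperature of > 38.3°C (101°F) or a sustained temperature of" 38°C or more for over 1 hour.

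**The concern.** A site managing a toxicity should be able to go from grade to action without guessing. Here the liver referral ends in a row that says what to measure but not what to do with the drug, and for one of the referred findings it does not even trigger the measuring. For neutrophils, two tables in the same section attach different recovery levels to restarting treatment, and one of them speaks of re-treatment at a grade where the other never stops it.

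At stake is patient safety first: the Phase 2 population has intrahepatic cholangiocarcinoma, where raised liver tests are a foreseeable question. Consistency comes second. The Phase 2 SAP summarises dose interruptions and reductions with their reasons (6.5.1.2) and AEs leading to discontinuation or dose modification (6.5.2.3, 6.5.2.4). If sites resolve the gaps differently, part of the variation in those tables reflects the site's reading of the protocol and not the toxicity.

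**Working it through.** No sample size, power or error rate is involved, so the check sets the rules side by side.

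**1. Neutrophils.** Table 8's bands are Grade 1, LLN to 1500/mm³; Grade 2, <1500 to 1000; Grade 3, <1000 to 500; Grade 4, <500.

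| Situation | Table 8 | Table 9 Hematology row |
|---|---|---|
| Grade 3 neutropenia | Dose kept, so nothing to restart | Test to Grade 1 or lower, or baseline, worded as permitting re-treatment |
| Grade 4 neutropenia | Withhold to Grade 2 or lower, or baseline | Grade 1 or lower, or baseline |
| Grade 3 or 4 thrombocytopenia | Withhold to Grade 1 or lower, or baseline | Grade 1 or lower, or baseline |

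The platelet rows agree, so the conflict is confined to neutrophils. After Grade 4 the tables differ when the recovered ANC is at least 1000 but below 1500/mm³ and baseline was better than Grade 2. If baseline was itself Grade 2, both are satisfied by return to baseline. Such patients can enrol, because inclusion criterion 7d (Protocol 7.2.1) admits an ANC of 1000/mm³ or more.

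**2. Which table governs restart.** Section 8.1.3.1.2 opens by saying that interruption and resumption criteria for hematologic toxicities are in Table 8. It later ties recovery within 21 days to Tables 6 through 8 and introduces Table 9 only for following toxicities until stabilization. The resumption criteria therefore sit outside Table 9, and its re-treatment wording contradicts them.

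**3. Possible size.** Take an assumed series with normal baseline: ANC 400 on Day 0, 1,100 on Day 6, 1,600 on Day 10. Table 8's level is met on Day 6 and Table 9's on Day 10. A site that followed Table 9's wording would restart 10 − 6 = 4 days later. Table 8's 7-day clock stops at Table 8's own recovery level, on Day 6. Since 6 ≤ 7, its instruction is to keep the dose level in either case.

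**4. Liver, case by case**, using the multiples printed in Table 9.
- Isolated Grade 2 ALT or AST: referred by Table 6, absent from the Hepatic row's triggers.
- Total bilirubin above 1.5 × but below 2 × ULN, alone: fractionation and work-up only.
- Bilirubin at least 2 × ULN, or Grade 2 bilirubin with Grade 2 ALT or AST: twice-weekly repeats and a recovery level, again worded as allowing re-treatment.

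None of the three comes with an instruction to hold, reduce or maintain. Other provisions do not fill the gap. The mandatory Medical Monitor discussion in 8.1.3.1.1 applies to Grade 3 or higher nonhematologic AEs. Table 6 footnote a gives discretion only for AEs thought unlikely to become serious or life-threatening.

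**5. Febrile neutropenia.** Take ANC 800/mm³ and a single reading of 38.4°C. Since 800 < 1000 and 38.4 > 38.3, Section 11.2.1 requires a febrile neutropenia report. Since 38.4 < 38.5, Table 8's febrile row is not met. The ANC lies between 500 and 1000, so the applicable row keeps the dose.

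**The case against.** The strongest reply is that Table 9 is a follow-up schedule and that the text itself names Tables 6 to 8 as the source of recovery and resumption criteria. That stands, and it rules out four stronger readings that a reader might infer.

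- *Table 9 is a second binding restart rule.* The documents do not say so. Its wording conflicts with the rule stated elsewhere.
- *The conflict changes the dose.* In the assumed series, a reader might count 10 days to recovery and conclude that the patient restarts at 16 mg instead of 20 mg. That puts Table 9's level into Table 8's 7-day clock, which no passage prescribes. The 21-day limit in 8.1.3.1.2 is likewise tied to Tables 6 to 8.
- *Table 9 has no dosing rules.* Its Cardiac row orders postponement and, if a mean QTcF above 500 ms is confirmed, permanent discontinuation. The gap is in the Hepatic row.
- *The febrile neutropenia definitions contradict each other.* One is a dosing trigger and the other a reporting definition, and a reporting threshold may deliberately be wider.

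It is also fair that the re-treatment wording in the Hematology row fits platelets, which Table 8 does withhold, and that None under Dose Adjustment in Table 6 could be read as covering Grade 2 liver elevations. Neither point settles the matter. The Hematology row names neutropenia without separating it from platelets. The None cell says nothing about interruption, and the cell beside it expressly removes these elevations from the instruction to maintain treatment.

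**Conclusion.** The inconsistencies are real and worth correcting, but limited. The liver referral matters most: sites are sent to a row with no dosing instruction, and for isolated Grade 2 ALT or AST to a row that does not mention the finding. The neutrophil conflict is one of wording. Its practical reach is a possible delay in restart after Grade 4, within an ANC of 1000 to <1500/mm³ and a baseline better than Grade 2, plus re-treatment wording at Grade 3 where dosing never stopped. The fever thresholds are secondary.

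This rests on the printed text of the tables and their linking sentences. The 4-day delay comes from an assumed ANC series and is not an estimate. The documents give no event rates, so how many patients would be affected cannot be stated, and no effect on the objective response rate has been shown. No view is taken on which threshold or rule is clinically right.

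**What to change.** Reconcile Tables 6, 8 and 9 so that:
- every referral leads to an explicit instruction, covering Grade 2 bilirubin, AST and ALT both alone and combined, or the exception pointing to Table 9 is removed;
- only one neutrophil recovery level is tied to re-treatment, and Table 9's re-treatment wording is confined to events that Tables 6 to 8 actually hold;
- Table 8 and Section 11.2.1 either use one febrile neutropenia definition or state that the difference between dosing trigger and reporting definition is intended.

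The sponsor chooses the thresholds and rules; none is proposed here. The cost is edits to three tables and one sentence, made through the amendment process in Protocol 14.1, with a memo to sites. No visits or tests are added.

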8.2. Description and Labeling

8.2.1. TAS-120

A description and packaging information for the study drug is described in [Table 10](#).

Table 10: TAS-120 Product description and packaging information

Product Description and Dosage Form	Potency/Strength	Appearance	Primary Packaging
TAS-120 Tablet	4 mg	Round, light yellow, film-coated tablet	Aluminum/Aclar blister

8.2.2. Packaging and Labeling

TAS-120 tablets will be packaged in child-resistant Dosepak[®] cards. Labeling will identify tablet counts in each card.

The Dosepak[®] cards will be labeled with at least the following:

- a. Protocol number
- b. Sponsor name
- c. Storage conditions
- d. Tablet strength
- e. Number of tablets in each container
- f. Investigational caution statement

Additional statements will be printed on the label(s) as required by local regulations.

8.2.3. Storage

TAS-120 tablets should be stored in accordance with the label. All study medication must be kept in a locked area with access restricted to specific study personnel.

8.2.4. Patient Instructions for Handling Study Drug

The patient must be instructed in the handling of TAS-120 as follows:

- To only remove the amount of TAS-120 needed at the time of dosing.
- Not to remove doses in advance of the next scheduled dosing.
- To bring all used and unused blister packs to the site at each visit.
- TAS-120 should be kept in a safe place and out of sight and reach of children.
- TAS-120 should be taken with a glass of water on an empty stomach (2 hours after and 1 hour before a meal).
- Doses are not to be replaced if the patient misses a dose or vomits a dose and administration of study drug should follow the direction of the treating physician.
- Patients should make every effort to take doses on schedule.
- To report any missed doses.

8.3. Drug Accountability

In accordance with International Council for Harmonisation (ICH) and local regulatory requirements, the investigator and/or the person responsible for dispensing investigational drug

must be able at all times to account for all investigational product provided to the site. The appropriate site personnel must acknowledge receipt of all TAS-120 either by forms included in each shipment or via other means (i.e., IXRS).

Dose reductions, interruptions, and reason for these actions must be recorded in the patient's source documents.

At the conclusion of the study, all used and unused TAS-120 shipped to the investigator must be returned to the Sponsor or designated Contract Research Organization (CRO). If on-site destruction is required by site policy, such requirements must be documented in the institution's Standard Operating Procedures (SOPs) and provided to the sponsor or its representative for review.

No TAS-120 is to be used outside of this study.

8.4. Blinding

This is an open-label study.

9. STUDY PROCEDURES

The study assessments are described by procedure in the following sections. All information required by the protocol must be recorded.

The study schedule must be followed; however, in unavoidable circumstances (e.g., holidays, weekends, etc.) a window of ± 3 days is allowable for study procedures as long as the proper order of procedures and assessments is maintained. The ± 3 -day window does not apply to assessments on Day 1 of Cycle 1.

For computed tomography (CT) scans, a window of ± 2 weeks (up to Cycle 4) or ± 7 days (all subsequent cycles) is allowable. These windows are not applicable during Screening. If any Screening assessments are repeated on Day 1 of Cycle 1 pre-dose, the site must ensure the patient meets the eligibility criteria listed in [Section 7.2](#), Study Population prior to the patient taking the first dose of TAS-120.

Note: Procedures performed during screening period within 72 hours prior to dosing on C1D1 do not need to be repeated on C1D1.

9.1. Pre-screening of Tumor Tissue Sample for FGFR2 Gene Fusions or other FGFR2 Rearrangements in Patients with iCCA (Phase 2 Only)

Archived or fresh tumor tissue biopsy samples will be tested for FGFR2 gene fusions or other FGFR2 rearrangements prior to enrolling patients to the Phase 2 part of the study.

Patients can be enrolled and treated based on the following:

- a. Testing by Foundation Medicine:
 - i. Sent to Foundation Medicine as part of study pre-screening; or
 - ii. Already tested by Foundation Medicine; in this case, it is requested that tumor tissue be sent to Foundation Medicine if available.
- b. Local laboratory testing using next generation sequencing [NGS], fluorescence in situ hybridization [FISH], or other assays that can determine FGFR2 gene fusions or other FGFR2 rearrangements on tumor tissues or from ctDNA. It is requested that patients enrolled on this basis provide tumor tissues to Foundation Medicine, if available from either archival samples or fresh tumor biopsy.

Testing may be performed at any time prior to enrollment into the study. -Results from the testing if not done as part of the TAS-120-101 protocol, must be maintained in the source files at the site.

Any AEs or serious adverse events (SAEs) directly associated with a pre-screening procedure (i.e., fresh tumor biopsy) should be reported as described in [Section 11.1](#). There is no need to record AEs and SAEs that occur between signing the pre-screening consent and full protocol consent if they are unrelated to the pre-screening tumor biopsy procedure unless it is mandatory by local regulations.

Tumor samples may be stored at the Sponsor's designated central laboratory for up to 10 years following completion of the study, to enable companion diagnostic research.

